From a physiological point of view, the goal of fluids is to increase SV and then CO and should only be given if the plateau of cardiac function is not reached in the individual patient (fluid responsiveness state). Fluid challenge (FC) is a diagnostic test consisting in the administration of a fixed volume of fluids with the purpose of identifying patients who will increase CO in response to fluid infusion [3, 12, 13]. Since several bedside clinical signs, systemic arterial pressure and static volumetric variables are poorly predictive of the effect of FC, the response to FC may be predicted at the bedside by using a functional hemodynamic test. This consists of a manoeuvre that affects cardiac function and/or heart-lung interactions, with a subsequent hemodynamic response, the extent of which varies between fluid responders and non-responders [14-16]. The combination of a functional hemodynamic test to assess fluid responsiveness and FCs to customize fluid infusion may be used to reduce the risk of fluid overload. Of note, at least 30% of the overall amount of fluid administered in septic patients may be related to the hidden and unintentional creep volume [17] (i.e. fluid administration not driven by a functional assessment of hemodynamics). In fact, a recent retrospective study on 14,654 patients during the cumulative 103,098 days showed that maintenance and replacement fluids accounted for 24.7% of the mean daily total fluid volume, thereby far exceeding

resuscitation fluids (6.5%) and were the most important sources of sodium and chloride. Fluid creep represented a striking 32.6% of the mean daily total fluid volume [median 645 mL (IQR 308-1039 mL)] [17].

Unfortunately, neither the FC nor the use of functional hemodynamic test are standardised in current clinical practice [18-21]. This was confirmed by the FENICE study, a large observational study on 2,213 patients conducted by the European Society of Intensive Medicine (ESICM) [19]. Since the first FENICE study publication, many activities have been provided by the ESICM in an effort to improve education and implementation of evidence-based haemodynamic management in intensive care unit (ICU) patients. These programs have focused on physiology, haemodynamic monitoring and interpretation, and fluid therapy. These efforts may have improved the use of functional hemodynamic tests and FC at bedside, with an impact on haemodynamic management and fluid administration policy in the ICU.

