- Evolvement of central venous pressure (Time Frame: up to day 5 - highest and lowest value)
- Evolvement of central venous oxygen saturation (Time Frame: up to day 5 - worst value)
- Evolvement of central venous to arterial carbon dioxide difference (Time Frame: up to day 5 - worst value)

Statistical analysis

Data will be described as median and interquartile range (IQR) or number and percentage. Categorical variables were compared using Fisher's exact test and continuous variables using the nonparametric Wilcoxon test, Mann-Whitney test, or Kruskal-Wallis test.

In way to assess volume of fluid received, group-based trajectory modeling (GBTM) will be used to identify clusters of patients with similar patterns of fluid administration profile. GBTM is a semiparametric technique used to identify distinct subgroups of individuals following a similar pattern of changes over time for a given variable [23]. To do so, we will use the R-software “kml” package that implements the k-means algorithm in context of longitudinal data [24]. Briefly, longitudinal change in fluid received each day from day 1 to day 3 will be assessed. In way to avoid misinterpretation of findings due to time dependent competing events such death or ICU discharge, this analysis will be performed on patients alive and still in the ICU at day 3. The optimal number of clusters was evaluated using Calinski & Harabasz criterion [25].

In way to assess impact of fluid administration strategy, factors associated with in-hospital mortality, including identified cluster of fluid administration, will be assessed using mixed logistic regression where in-hospital mortality will be event of interest. Variables of interest will be selected according to their relevance and statistical significance in univariate analysis. We will use conditional stepwise regression with 0.2 as the critical P-value for entry into the model, and 0.1 as the P-value for removal. It will be planned a priori to force identified clusters and relevant variable related to hemodynamic instability in the model. Last, the center effect will be included as a random effect against the intercept. Should a center effect be identified, a secondary analysis in line with centers characteristics will be performed. Interactions and correlations between the explanatory variables will be checked. Continuous variables for which log-linearity will not confirmed, will be transformed into categorical variables according to median or IQR.

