For secondary outcomes, and in particular for day-30 mortality, number of days alive without vasopressors, mechanical ventilation or renal replacement therapy, will be assessed using survival analysis.

All tests will be two-sided, and P-value less than 0.05 will be considered statistically significant. Analyses will be performed using R software version 3.4.4 (<https://www.r-project.org>), including ‘kml’, ‘caret’, ‘lme4’, and ‘lmerTest’ packages.

Sample size

Considering the results of the FENICE study, we plan to enrol 10,000 patients and 15,000 FCs [30 patients / centre (max) and > 300 centres (min)]. The planned number of patients to be enrolled is in line with previous similar large observational trials regarding the use of fluids in ICU patients with the purpose of assessing current clinical practice and potential impact on clinical outcomes.

Data imputation

No data imputation will be performed on main outcome variables. Patients discharge alive from hospital, not admitted in rehabilitation unit or palliative care unit and/or lost of sight will be considered alive and free from organ support until day 30. Missing daily fluid volume will be imputed only if available every other day in which case it will be averaged.

Sensitivity analyses

In way to assess impact of fluid administration strategies, fluid volume considering only high chloride concentration fluids and impact of hypotonic fluids, three dedicated analyses using same methods than main analysis will be performed.

Ethical considerations and personal data protection

Patient protection

The responsible investigator will ensure that this study is conducted in agreement with either the Declaration of Helsinki or the laws and regulations of the country. The protocol has been written, and the study will be conducted according to Guideline for Good Clinical Practice. The protocol and its annexes are subject to review and approval by the competent Independent Ethics Committee(s) (“IEC”).

Subject identification

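### The high-chloride and hypotonic sensitivity analyses do not require total fluid volume in the model, so their results may reflect how much fluid was given rather than which fluid

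*Protocol*

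**What the plan says.** The Sensitivity analyses section of the protocol names fluid strategies, high-chloride fluids and hypotonic fluids, and gives all three the main-analysis treatment: "fluid volume considering only high chloride concentration fluids and impact of hypotonic fluids, three dedicated analyses using same methods than main analysis will be performed".

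The Statistical analysis section defines that treatment.

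- **Exposure:** "In way to assess volume of fluid received, group-based trajectory modeling (GBTM) will be used to identify clusters of patients with similar patterns". The window is short: "longitudinal change in fluid received each day from day 1 to day 3 will be assessed".
- **Analysis set:** "this analysis will be performed on patients alive and still in the ICU at day 3".
- **Outcome model:** factors associated with death, the clusters among them, "will be assessed using mixed logistic regression where in-hospital mortality will be event of interest".
- **Forced terms:** "It will be planned a priori to force identified clusters and relevant variable related to hemodynamic instability in the model".
- **Other covariates:** chosen by relevance and univariate significance, then stepwise with P-values of 0.2 for entry and 0.1 for removal. Correlations among covariates are to be checked, with no rule on which of two correlated terms to keep.

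Total volume, the volume of the other fluids, and the high-chloride or hypotonic share are neither named as model terms nor excluded. The Introduction gives a reason to care about composition: in a cited retrospective study, maintenance and replacement fluids "were the most important sources of sodium and chloride".

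**The concern.** High-chloride volume is one component of total volume. A patient given more of everything also tends to be given more high-chloride fluid, and clustering on its absolute volume will tend to place that patient in the high-chloride cluster. If total volume is associated with in-hospital mortality after the other covariates, the cluster inherits some of that association whether or not chloride matters.

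These are the only models in the protocol built around a fluid type. A positive result would invite the conclusion that high-chloride fluid is associated with death, when it might be the main volume finding under a different label.

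**Working it through.** The plan has no figure to reproduce here. It states no effect size, mortality rate, high-chloride share or correlation between fluid volumes. The planned 10,000 patients have no power calculation behind them, and the point does not depend on that number. The structure comes from the protocol; the size can only be illustrated on assumed inputs.

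**Structure.** For patient i on day d, high-chloride volume = share(i) × total volume(i, d). It therefore varies with total volume even when share and total are independent. The planned model contains the cluster of this product and the instability variables, plus whatever the stepwise step retains.

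**Assumed inputs.**

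- Analysis set of 5,000 or 8,000 (the number alive and in ICU at day 3 is not stated).
- Daily volume log-normal, median scale 2.2 L, with day multipliers 1.3, 1.0 and 0.8, higher in sicker patients.
- High-chloride share independent of total volume, centred at 0.5 or 0.3, with three degrees of spread. These give correlations of 0.89, 0.75 and 0.54 between high-chloride and total volume.
- log-odds of death = −1.3 + 0.5 × severity + b₁ × (standardised log total volume) + b₂ × (standardised share), giving mortality of about 23%.

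**Analysis.** Two-cluster k-means on the three daily high-chloride volumes, then logistic regression of death on cluster and severity, with and without log total volume; 200 runs per setting. The centre effect, the stepwise step and the choice of cluster number were not simulated.

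**Results.** Odds ratio (OR) for the high-chloride cluster, with the percentage of runs at P<0.05 in brackets. Percentages are for 5,000 then 8,000 patients; ORs are given as a pair where the two sizes differ.

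| What raises mortality (OR per SD) | Correlation | Total volume out | Total volume in |
|---|---|---|---|
| Amount only, 1.20 | 0.89 | 1.26 (78, 94) | 1.01, 1.00 (4, 7) |
| Amount only, 1.20 | 0.75 | 1.22, 1.21 (68, 82) | 1.01, 1.00 (6, 4) |
| Amount only, 1.20 | 0.54 | 1.16 (39, 61) | 1.01, 1.00 (6, 5) |
| Amount only, 1.11 | 0.89 | 1.14 (38, 54) | 1.01, 1.00 (3, 7) |
| Amount only, 1.11 | 0.75 | 1.11 (27, 41) | 1.01, 1.00 (4, 4) |
| Amount only, 1.11 | 0.54 | 1.09 (16, 26) | 1.01 (6, 5) |
| Type only, 1.20 | 0.89 | 1.16 (45, 63) | 1.28 (65, 81) |
| Type only, 1.20 | 0.75 | 1.23 (71, 87) | 1.34 (84, 96) |
| Type only, 1.20 | 0.54 | 1.33 (95, 99) | 1.41, 1.40 (98, 100) |
| Neither | 0.54 to 0.89 | 1.00 (3 to 9) | 1.00 to 1.01 (3 to 7) |

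With 200 runs, the simulation standard error of a 5% rate is √(0.05 × 0.95 / 200) = 0.015.

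**Reading.** With total volume out, a pure amount effect gives 1.09 to 1.26 and a pure type effect gives 1.16 to 1.33. The ranges overlap, so the cluster OR alone does not show which is acting. With total volume in, the amount-only OR falls to 1.00 to 1.01, while the type-only OR stays at 1.28 to 1.41. Using the share (above or below its median) as exposure, with total volume as covariate, gives 1.00 to 1.01 when only amount acts (P<0.05 in 3 to 5% of runs) and 1.34 to 1.37 when only type acts (98 to 100%).

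**The case against.** The strongest reply is that the protocol never says total volume is left out. Selection is open, total volume can be computed from the data collected, and a full covariate list may sit in a statistical analysis plan that is not shown. If total volume were offered, it would probably stay. In a simpler version of the simulation (OR 1.10 per litre, about 18% mortality), its P-value was below the 0.1 removal threshold in 60 of 60 runs at each setting. This stands against any claim that the plan excludes total volume. It does not remove the point: the protocol itself fixes the exposure as an absolute volume, nothing makes total volume a candidate, and the correlation check could discard it because it is correlated with the exposure.

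A reader might infer more than the documents support:

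- **That type and amount cannot be separated.** They can, once total volume or the share is modelled.
- **That a false association is bound to appear.** It needs total volume to be associated with mortality; with neither effect present the OR was 1.00. The Introduction cites two randomised trials in which a restrictive strategy was non-inferior to a liberal one, so a causal volume effect is not a given. An observational association, for instance through residual severity, would be enough to produce the bias.
- **That the false OR is as large as 1.40 to 1.55.** Such values arise with a median split, no severity covariate and all 10,000 patients, none of which matches the plan.
- **That the hypotonic analysis is equally exposed.** The text speaks of impact, not volume, so volume clustering is read in through the reference to the same methods. For a fluid making up 10 to 15% of the total, the simpler simulation gave a correlation near 0.43 and a false OR near 1.20, against 1.40 to 1.55 for high-chloride fluid at a 50% share.
- **That serum sodium and chloride are wrongly missing.** The case report form is not shown, so their absence from the outcome list proves nothing.

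These are also sensitivity analyses in a study whose primary aim is descriptive, and the Endpoints section has a general aim on fluid characteristics and outcomes. That limits the stakes, but it supplies no other fluid-type model.

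**Conclusion.** The point holds in limited form. As specified, the high-chloride analysis does not require the adjustment needed to read its result as an effect of fluid type, and the hypotonic analysis shares the weakness, less strongly, if it is run on volume. If total volume is associated with mortality (1.11 to 1.20 per SD) and stays out of the model, the false OR is about 1.09 to 1.26, significant in 16 to 94% of runs. Including total volume brings it to about 1.00.

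All of these sizes rest on assumed volumes, shares, mortality and analysis-set size, and on share being independent of total volume. The direction of the problem follows from the exposure definition alone.

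**What to change.** In Sensitivity analyses, state one of the following for the high-chloride and hypotonic models:

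- total IV fluid volume over days 1 to 3 is forced into the model beside the fluid-type cluster; or
- the exposure is the high-chloride (or hypotonic) share of total volume, with total volume as covariate.

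In either case, exempt total volume from stepwise removal and from deletion after the correlation check. Keep it continuous, as in the simulated correction: the protocol's fallback of cutting variables at the median or IQR would leave differences in amount within categories. The fluid-type coefficient then compares patients given the same total volume but different fluids, and should be reported that way. State also whether the hypotonic exposure is a volume or a share.

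The cost is a sentence or two and one covariate derived from volumes the protocol already collects. The drawback is somewhat wider intervals, because fluid-type volume and total volume are correlated.
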